9.2.7 Subject Withdrawal and Discontinuation

Subjects may voluntarily withdraw (ie, reduce the degree of participation in the study) consent for continued participation and data collection. The reason for withdrawal will be recorded on the End of Study CRF. The data collected on withdrawn subjects will be used in the analysis up to the date of withdrawal and included in the study report.

Discontinuation (ie, complete withdrawal from study participation) may be due to dropout (ie, active discontinuation by subject) or loss to follow-up (ie, discontinuation by subject without notice). Additionally, the investigator may decide to discontinue any subject from the study.

9.2.8 Study Stopping Rules

Stopping rules will not be established for this study.

9.3 Variables

9.3.1 Variables for assessing the primary endpoint

9.3.1.1 Effectiveness of prophylaxis

- Effectiveness as measured by
 - Overall effectiveness assessment for the prevention of bleeding
 - ABR and monthly bleeding rate (MBR), all bleeds
 - AJBR, monthly joint bleeding rate, all joint bleeding events
 - ABR, MBR, trauma related
 - Overall effectiveness assessment for prophylaxis with an “excellent-to-poor” 4-point scale, as rated by the patients or care-giver (for details, see Appendix 1, [Table 4](#)).

9.3.2 Variables for assessing the secondary endpoints

9.3.2.1 Effectiveness of on-demand treatment

(see [APPENDIX 1](#))

- Overall effectiveness assessment for on-demand treatment with an “excellent-to-poor” 4-point scale, as rated by the patients or care-giver, also a rating of the severity of bleeding (mild, moderate, severe) (for details, see Appendix 1, [Table 3](#))
- Total weight-adjusted dose required for bleeding episode resolution
- Number of rFIX (RIXUBIS) infusions required for bleeding episode resolution.
- For perioperative treatment:
 - Type and severity of the surgical intervention
 - Intraoperative and postoperative effectiveness according to an “excellent-to-poor” 4-point scale (surgery) assessed by the physicians
 - Total weight-adjusted dose and number of infusions of rFIX (RXUBIS) required to cover the surgical procedure
 - Number of days spent in hospital related to the surgery
 - Need for supplemental hemostatic therapy (i.e. tranexamic acid, etc.).

9.3.2.2 Safety and Immunogenicity

- Incidence of inhibitors in PTPs with history of inhibitors and with FIX <1%, ≤2% and >2-5%
- Incidence of inhibitors in PTPs without history of inhibitors and with FIX <1%, ≤2% and >2-5%
- Incidence of inhibitors in previously untreated patients (PUPs) with FIX <1% and ≤2% and >2-5%
- Treatment regime after an inhibitor has occurred in PUPs and PTPs
- Incidence and severity of SAE and NSAE
- Incidence and severity of therapy-related SAE and NSAE
- Incidence of life-threatening bleeding episodes
- Incidence of thromboembolic events.

9.3.2.3 Joint Health/Function Outcomes

(see [APPENDIX 2](#))

The health status of the joints (e.g. knee, ankles, elbows) will be further assessed by the following endpoints, where available

- HJHS ¹⁷
- Radiographs, using the Pettersson scale ¹⁸
- Magnetic resonance imaging scoring system
- Total number of target joints ¹⁹
- Number of invasive surgical procedures, such as (not exclusively orthopedic) surgery, radiosynovectomy, and chemosynovectomy per year per patient
- Incidence of new target joints

A target joint is defined as a joint in which at least 3 or more spontaneous bleeds into a single joint within a consecutive 6 month period. Where there have been ≤ 2 bleeds into the joint within a consecutive 12 month period the joint is no longer considered a target joint ¹⁹.

9.3.2.4 Health-Related Quality of Life Variables

9.3.2.4.1 Health-Related Quality of Life Questionnaires (HRQoL Questionnaires)

- HRQoL questionnaires in subjects receiving rFIX (RIXUBIS) will be provided at the screening visit and on an annual basis to subjects or their legally authorized representatives. QoL questionnaires may not be available in all languages and therefore will not be available at all study sites.
- SF-12 version 2.0 (SF-12v2), and EQ-5D questionnaires – for adult subjects ≥ 18 years
 - The SF-12v2 is a self-administered generic measure of HRQoL derived from the SF-36. It covers the same 8 health domains as the SF-36v2 with one or two questions per domain, and yields 8 domain scores as well as two Physical and Mental Component Summary measures, referred to as PCS-12 and MCS-12. The recall period is the past 4 weeks. A higher score indicates better QoL.
 - The EQ-5D is a generic instrument developed by the EuroQoL group to assess subject's health status for clinical and economic appraisal. The EQ-5D is a self-administered instrument composed of two parts. The first part is a descriptive system consisting of five dimensions: mobility, self-care, usual activities, pain/discomfort and anxiety/depression. Each dimension has 3 levels of severity: no problems, some problems, extreme problems.

Responses to the five dimensions are combined and converted into a single preference-based health utility index by applying value sets. The second part is a 20-cm vertical visual analog scale (EQ-VAS) to rate one's current HRQoL, anchored at 0 and 100 for worst and best imaginable health states, respectively. For either part, the recall period is the present time. A higher score indicates better QoL.

- SF-10, is a generic measure of functional health and well-being for children aged 5-18 and is parent-completed. The SF-10v2 contains ten items adapted from the Child Health Questionnaire that estimate scores for a Physical (PHS) and a Psychosocial (PSS) Summary Measures. The recall period is the past 4 weeks. A higher score indicates better QoL.
- EQ-5D-Y (Youth version). is a generic measure of health status designed for children aged 7-12, and is completed by the parent or legal guardian. Descriptive system of youth health-related quality of life states consisting of five dimensions (mobility, looking after myself, doing usual activities, having pain or discomfort, feeling worried, sad or unhappy) each of which can take one of three responses. The responses record three levels of severity (“no problem,” “some or moderate problems,” “extreme problems/impossible to do”) within a particular EQ-5D-Y dimension. The recall period is the present time. A higher score indicates better QoL.
- HaemoQoL scale for both adults (Haem-A-QoL > 18 years) and children (HaemoQoL) aged 4-17. Patients are to fill out the questionnaire version for their child's age at the current annual visit.
 - The Haemo-QoL is a disease-specific HRQoL assessment instrument for children and adolescents with hemophilia. There are 3 sets of psychometrically tested questionnaire versions of variable length for three age groups of children, as well as their parents/ legally authorized representative. In addition to the full version, a short version for small children (4-7 years) containing 16 items and a short version for older children (8-16 years) containing 35 items have been developed. An 8-item index version was developed spanning all age groups which is also available for completion by the pediatric patient or their parent/ legally authorized representative. The questionnaires yield domain scores and a total score. A higher score indicates greater impairment.
 - The Haem-A-QoL is a disease-specific HRQoL assessment instrument designed for adult patients with hemophilia. It consists of 46 items pertaining to 10 dimensions (physical health, feelings, view of yourself, sport and leisure, work and school, dealing with hemophilia, treatment, future, family planning, partnership and sexuality). It yields domain scores and a total score. A higher score indicates greater impairment.

9.3.2.4.2 Acute and Chronic Pain

Acute and chronic pain in subjects receiving rFIX (RIXUBIS) will be assessed.

- Acute pain associated with hemophilia, as measured by individual bleeding episodes, using the Numeric Rating Scale (NRS) or Pediatric “Wong Baker Face Scale” as appropriate
- Chronic pain [defined as “Continuous and/or intermittent pain, related to the pathophysiology of hemophilia, requiring intervention (pharmacological or non-pharmacological pain treatment), in which the cause of pain cannot be readily removed, occurring more than once a week and lasting 3 months or more”] associated with hemophilia²⁰, if available, assessed by the Numeric Rating Scale (NRS) or Pediatric “Wong Baker Face Scale” as appropriate.

- **Numeric Rating Scale**

The numeric rating scale (NRS) is a unidimensional measure of pain intensity in adults. The most commonly iteration used is the 11 item NRS. The common format is a horizontal bar or line. Similar to the pain Visual Analog Scale (VAS), the NRS is anchored by describing pain severity extremes. It can be administered either verbally or graphically for self-completion and the subject is asked to indicate the numeric value on the segmented scale that best describes pain intensity.

- Pediatric subjects or subjects who have difficulty quantifying their pain numerically can be asked to assess the pain by using the following Wong Baker Face Scale.

Explain to the individual that each face is for an individual who feels happy because he has no pain (hurt) or sad because he has some or a lot of pain. Face 0 is very happy because he does not hurt at all. Face 1 hurts just a little bit. Face 2 hurts a little more. Face 3 hurts even more. Face 4 hurts a whole lot. Face 5 hurts as much as you can imagine, although the individual does not have to be crying to feel this bad. Ask the individual to choose the face that best describes how he is feeling. This rating scale is recommended for individuals 3 years and older. Brief instructions: point to each face using the words to describe the pain intensity. Ask the individual to choose the face that best describes the pain and record the appropriate number.

During the screening and on an annual basis – or more frequently based on the standard practice at the site - the investigators shall ask subjects to rate the average level of chronic pain associated with hemophilia over the period of 4 weeks prior to visit date using the NRS or Pediatric “Wong Baker Face Scale” as appropriate. The scores will be recorded in the subject diary on a voluntary basis.

9.3.2.4.3 Physical Activity Level

- Daily activity level, if available, will be assessed by the Hemophilia Activity Level scale (HAL) ^{21,22} in adults and Pediatric Hemophilia Activity Level scale (PedHAL) in children. The HAL measures activities involving the upper extremities, basic activities involving the lower extremities, and complex activities involving the lower extremities, as well as an overall physical activity score for adults. The aim of this questionnaire is to determine the ability of the subject to perform the listed activities:

- Lying down/ sitting / kneeling / standing
- Functions of the legs
- Functions of the arms
- Use of transportation
- Self-care
- Household tasks
- Leisure activities and sports
- Adaptations and using an aid.

There are six different response options (impossible, always, mostly, sometimes, rarely, never) for each type of activity. For activities, the recall period is the past month. The HAL yields 7 domain scores and an overall score. A higher score represents more functional limitations.

- The pedHAL measures a number of activities involving the upper extremities, basic activities involving the lower extremities, and complex activities involving the lower extremities, as well as an overall physical activity score for children. The aim of this questionnaire is to determine the ability of children to perform the listed activities:

- Lying down/ sitting / kneeling / standing
- Functions of the legs
- Functions of the arms
- Use of transportation
- Self-care
- Household tasks
- Leisure activities and sports
- Adaptations and using an aid.

Parent/proxy (age 4-8) and child (8-18) versions are available. There are six different response options (impossible, always, mostly, sometimes, rarely, never) for each type of activity. For activities, the recall period is the past month. The pedHAL yields 7 domain scores and an overall score. A higher score represents more functional limitations.

9.3.2.4.4 Haemophilia-related comorbidities

The following will be recorded:

- Incidence of target joint intervention, including surgery, radiosynvectomy and chemosynvectomy.
- Incidence of pseudotumor development.

9.3.2.4.5 Healthcare resource use

Healthcare resource use in subjects receiving rFIX (RIXUBIS) will be assessed to estimate health-related direct and indirect costs if applicable in the country. Also, additional resources which are available at the hemophilia treatment center and routinely used by the subject will be assessed. Direct medical costs, direct non-medical costs and indirect costs (if applicable and available) will be appraised by the valuation of the following resources:

- number of home care nursing visits
- number of physiotherapy sessions
- number of orthopedic consultations
- number of nutritional guidance and training sport/school counseling sessions
- number of psychological support/counseling sessions
- number of social counseling sessions
- number of social support (e.g. disease communicator/trouble shooter) visits
- number of visits for emergency FIX stock available at center
- number of 24h hotline calls available at center
- number of phone counseling sessions of patients
- number of laboratory diagnostics visits available at center
- number of dental consultations
- number of infectiology (immunological counseling) sessions

- usage of an electronic diary/smart phone application (e.g. Smart Medication)
- financial help for center visits (travel expense reimbursement)
- number of patient education (e.g. injection training) sessions
- number of scheduled and unscheduled visits at the site
- number of ER visits
- number of inpatient hospitalization, length of stay and severity of complication related to hemophilia (excluding planned surgery)
- length of stay in the hospital per inpatient hospital and severity/kind of complication
- number of days the subject cannot follow normal daily routine (e.g. school, work) due to bleeding episodes or their treatment.

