Pharmacokinetics, safety and efficacy has been shown in a phase I/III clinical study in previously treated patients (PTPs) with severe (<1% FIX) and moderately severe ($\leq 2\%$ FIX level).^{1,3} RIXUBIS was safe and well tolerated in all 73 patients in the full analysis set. AEs considered related to treatment (2.7% incidence) were mild and transient. No hypersensitivity reaction, inhibitor formation or thrombotic events were observed. PK equivalence of RIXUBIS in comparison to an already licenced recombinant FIX was evaluated by comparing the ratio of the geometric mean of the area under the curve (AUC) per dose over the 0-72h period. Twice weekly prophylaxis (mean 49.5 IU/kg/dose) was effective in preventing bleeding episodes with a significantly lower (by 79%) annualized bleeding rate (ABR) compared to a historical group treated on-demand (4.2 Vs 20.0). Of the subjects on prophylaxis, 43% (24/56) did not bleed throughout the duration of the study. Of 249 acute bleeds, 211 (84.7%) were controlled with 1 or 2 infusions of RIXUBIS. Hemostatic effectiveness was rated excellent or good in 96% of all treated bleeding episodes. The results of this study indicate that RIXUBIS treatment is safe and efficacious in treating bleeds and as routine prophylaxis in patients aged 12 years and older with hemophilia B^{2,3}.

Additionally, this clinical trial assessed aspects of quality of life (QoL) of hemophilia B patients². Health-related QoL (HRQoL) burden of hemophilia B, the benefit of RIXUBIS prophylaxis and the HRQoL benefits of achieving a zero annual bleed rate was investigated. Short-Form Health Survey (SF-36) scores showed statistically significant and clinically meaningful improvements in overall physical HRQoL measured by the Physical Component Summary (PCS) score, Bodily Pain (BP) and Role Physical (RP) domains. Subjects that switched to prophylaxis from intermittent prophylaxis or on-demand treatment experienced more pronounced improvements not only in PCS, BP and RP scores, but also in Vitality (VT), Social Functioning (SF) and General Health (GH) domains. Subjects achieving zero bleeds reported reduced BP scores. Therefore prophylaxis with RIXUBIS improved HRQoL in patients with moderately severe and severe hemophilia B by reducing bleeds.

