8.3 Secondary Objectives

- To describe hemostatic effectiveness in the treatment of bleeding events in subjects with hemophilia B receiving rFIX (RIXUBIS).
- To describe the safety and immunogenicity in subjects with hemophilia B receiving rFIX (RIXUBIS).
- To describe joint health outcomes in subjects receiving rFIX (RIXUBIS).
- Health-Related Quality of Life (HR-QoL) objectives:
 - To describe HRQoLin subjects receiving rFIX (RIXUBIS)
 - To describe acute and chronic pain associated with hemophilia in subjects receiving rFIX (RIXUBIS)
 - To describe the physical activity in subjects receiving rFIX (RIXUBIS)
- To describe hemophilia-related co-morbidity in subjects receiving rFIX (RIXUBIS)
- To describe healthcare resources use in subjects receiving rFIX (RIXUBIS) on-demand or prophylactically.

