9.7.3.3 Methods of Analysis for Effectiveness Criteria

The annualized rate of bleeding episodes in joints, target joints, and other anatomical locations for the two independent samples (on-demand or prophylaxis) will be summarized. The frequency distribution for the number of infusions for bleed treatment will be reported for each of the on-demand and prophylaxis treatment regimens. The median number of infusions per bleeding episode for each subject will be calculated and the median for subjects in each treatment regimen will be compared using the Mann-Whitney (Wilcoxon-Rank Sum) test. The total weight-adjusted dose (IU/kg) per bleeding episode per subject will be described for both the on-demand and prophylaxis treatment regimens and will be compared using the Mann-Whitney (Wilcoxon-Rank Sum) test.

Corresponding to all treated FIX (RIXUBIS) bleeding episodes, the following parameters will be computed separately by treatment regimen (prophylaxis, on-demand):

Total number of subjects infused
Total bleed exposure days
Total number of bleed treatment infusions
Units administered per subject, per infusion (IU)
Units administered per subject, per bleed (IU)
Annualized units administered for bleed treatment, per subject (IU)
Total units administered for bleed treatment, per subject (IU)
Weight-adjusted dose per subject, per bleed (IU/kg)
Weight-adjusted dose per subject, per infusion (IU/kg)
Annualized weight-adjusted dose for bleed treatment, per subject (IU/kg)
Total weight-adjusted dose for bleed treatment, per subject (IU/kg)

Assessment of effectiveness:

Corresponding to subjects given prophylactic infusions (RIXUBIS) in this study, the following parameters will be computed by treatment regimen (prophylaxis, on-demand):

Total number of subjects infused
Total exposure days
Total number of infusions
Number of unique lots used
Units administered per subject, per infusion (IU)
Units administered per subject, per week (IU)
Units administered per subject, per month (IU)
Annualized units administered, per subject (IU)
Total units administered, per subject (IU)
Weight-adjusted dose per subject, per infusion (IU/kg)
Weight-adjusted dose per subject, per week (IU/kg)
Weight-adjusted dose per subject, per month (IU/kg)
Annualized weight-adjusted dose, per subject (IU/kg)
Total weight-adjusted dose, per subject (IU/kg)

The occurrence of new target joints and bleeding episodes used to assess new target joints will be summarized by treatment regimen.

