9.7.3.4.5 Methods of Health Resource Use Related (HRUR) Endpoints Analysis

All HRUR parameters will be summarized by treatment regimen (on-demand, prophylaxis). If available, changes from baseline to each follow-up study visit will be summarized by treatment regimen.

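### The list of resources to be valued as costs omits factor IX concentrate, so a direct medical cost built from it would be understated in both regimens, and more so under prophylaxis

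*Protocol*

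**What the plan says.** The secondary objective in Protocol 8.3 is "To describe healthcare resources use in subjects receiving rFIX (RIXUBIS) on-demand or prophylactically". Section 9.3.2.4.5 gives resource use an economic purpose: it "will be assessed to estimate health-related direct and indirect costs if applicable in the country". It then says how this is done: "Direct medical costs, direct non-medical costs and indirect costs (if applicable and available) will be appraised by the valuation of the following resources". A list of 21 items follows. The only entry that mentions the product is "number of visits for emergency FIX stock available at center", which counts visits and not units.

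Section 9.7.3.4.5 sets the reporting: "All HRUR parameters will be summarized by treatment regimen (on-demand, prophylaxis").

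FIX consumption is planned elsewhere. Section 9.7.3.3, under effectiveness, lists "Annualized units administered for bleed treatment, per subject (IU") for treated bleeds and "Annualized units administered, per subject (IU") for prophylactic infusions, both by regimen. Section 9.3.2.1 collects the weight-adjusted dose used to cover surgery and the related hospital days. Section 9.2.1 has regimen, dose and frequency recorded in the e-CRF. No section carries any of these into the cost valuation.

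**The concern.** Annex 14.3 separates the regimens by how concentrate is given: regularly, at least once a week, for prophylaxis, and for acute bleeds when on-demand. Concentrate use is thus the resource on which the two groups differ by definition, and it is the one not valued. The lead-in sentence reads as a closed list, so this is something the protocol fixes and not a detail left open for a later analysis plan. The sentence on additional resources does not repair it, because it concerns services available at the treatment centre.

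A figure presented as direct medical cost, set out by regimen, would therefore leave out the study product. Readers of an economic description would not expect that, and the size of the gap would depend on the regimen.

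**Working it through.** **Inputs from Protocol 7.2 (pivotal study).** "Twice weekly prophylaxis (mean 49.5 IU/kg/dose) was effective in preventing bleeding episodes"; annualised bleeding rate 4.2 on prophylaxis against 20.0 in a historical on-demand group; 211 of 249 bleeds controlled with 1 or 2 infusions.

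**Assumption.** The dose per bleed infusion, d, is not given there. I take 40 to 60 IU/kg, with 80 as a wider bound. Infusions per bleed, k, are taken as 1 to 2.

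**1. Reproduce the stated figures.** Bleed-rate reduction: 1 − 4.2/20.0 = 79.0% (stated 79%). Bleeds controlled with 1 or 2 infusions: 211/249 = 84.7% (stated 84.7%).

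**2. Prophylactic infusions alone.** 2 × 49.5 × 365.25/7 = 5,166 IU/kg/year.

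**3. Annual FIX volume by regimen.** On-demand = 20.0 × k × d. Prophylaxis = 5,166 + 4.2 × k × d.

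| d (IU/kg) | k | On-demand | Prophylaxis | Difference | Ratio |
|---|---|---|---|---|---|
| 40 | 1 | 800 | 5,334 | 4,534 | 6.7 |
| 40 | 2 | 1,600 | 5,502 | 3,902 | 3.4 |
| 49.5 | 1 | 990 | 5,374 | 4,384 | 5.4 |
| 49.5 | 2 | 1,980 | 5,581 | 3,601 | 2.8 |
| 60 | 1 | 1,200 | 5,418 | 4,218 | 4.5 |
| 60 | 2 | 2,400 | 5,670 | 3,270 | 2.4 |
| 80 | 2 | 3,200 | 5,838 | 2,638 | 1.8 |

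**4. When would the volumes be equal?** k = 5,166 / ((20.0 − 4.2) × d), which is 8.2 infusions per bleed at d = 40, 6.6 at 49.5, 5.4 at 60 and 4.1 at 80.

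**5. Sensitivity to the prophylaxis intensity.** Annex 14.3 accepts one administration a week as prophylaxis. At 49.5 IU/kg once weekly the infusions come to 49.5 × 365.25/7 = 2,583 IU/kg/year. Keeping the same bleeding rates, d = 60 and k = 2 give 2,583 + 504 = 3,087 against 2,400, a ratio of 1.3. The volumes are then equal at 2,583 / (15.8 × 60) = 2.7 infusions per bleed. The direction holds for 1 to 2 infusions, but the margin is much smaller.

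**6. Cross-check from Protocol 7.1.** In the four earlier studies prophylaxis took 40,172,963 / 50,756,155 = 79.1% of all units.

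**7. Hospital-stay items in 9.3.2.4.5.** One item, covering admissions, length of stay and severity of complication, excludes planned surgery. The next, on length of stay per admission, carries no exclusion. As written, it is unclear whether days for planned surgery are valued.

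**The case against.** The strongest reply is that no total cost by regimen is planned. Section 9.7.3.4.5 summarises resource-use parameters, the objective is to describe resource use, and costing appears only in 9.3.2.4.5, where it is made conditional on applicability and availability. Prices, perspective and aggregation may be in an analysis plan that is not at hand. FIX units by regimen will be reported anyway under 9.7.3.3, so a reader could put the two together. The analysis is descriptive, in an uncontrolled study without hypothesis tests.

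Much of this stands, and it rules out several stronger readings that a reader might infer:

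- That prophylaxis would wrongly come out cheaper. A reversed sign needs a price per unit and service costs, and the protocol gives neither. Only volume and direction can be checked.
- That only prophylaxis loses its input. FIX is missing from the list for both regimens, so any distortion is the net difference.
- That the list mostly counts savings from fewer bleeds. About five of the 21 items are plainly bleed-driven (emergency room visits, admissions, length of stay, lost days, perhaps emergency-stock visits). Most of the rest are services that the protocol does not tie to bleeding, and some could rise with regular infusions.
- That planned-surgery stays are excluded altogether. The exclusion sits in one item only, and 9.3.2.1 collects surgical hospital days separately.

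The volumes are also illustrative: the on-demand rate is historical, the pivotal study enrolled severe and moderately severe patients, and this study admits FIX levels up to 5%.

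The reply does not put FIX on the list. Section 9.3.2.4.5 says what will be valued to obtain direct medical costs, and the study product is not there.

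**Conclusion.** The point holds as a defect in the definition of the cost output. Any direct medical cost built from the list in 9.3.2.4.5 would be understated in both regimens and, on the protocol's own pivotal figures, more so under prophylaxis. The difference left out is about 3,270 to 4,534 IU/kg/year, a ratio of 2.4 to 6.7. This rests on twice-weekly dosing at 49.5 IU/kg, bleeding rates of 4.2 and 20.0 per year, and the assumed 1 to 2 infusions of 40 to 60 IU/kg per bleed. It shrinks if prophylaxis is given less often. What this means in money, and whether a cost contrast would reverse, cannot be determined from the protocol.

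The matter concerns a conditional, descriptive secondary item and touches no primary or safety conclusion. It is still worth correcting, because the omission is explicit, it differs by regimen, and the missing data are already planned.

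**What to change.** In 9.3.2.4.5, add FIX consumption to the valued resources, as units per subject-year for prophylaxis, bleed treatment and surgery. Do this by cross-reference to the annualised units in 9.7.3.3 and the surgical dose in 9.3.2.1.

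If concentrate is left out on purpose, say so, label the output as costs excluding FIX product, and report no total direct medical cost by regimen.

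In either case, reconcile the two hospital-stay items so that it is clear whether days for planned surgery are valued.

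The cost is a few lines of wording and one more summary row, with no new data collection. The downside for the sponsor is a less favourable economic picture for prophylaxis.
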